There is no clear consensus regarding appropriate control conditions to use in alcohol reduction app (Staiger, O'Donnell, Liknaitzky, Bush, & Milward, 2020) or ApBM research (Kakoschke, Kemps, & Tiggemann, 2018). In designing our control condition, a primary consideration was controlling for the effect of self-monitoring, since the data collection aspects of AAT-App involve regular self-report of alcohol use, and such self-monitoring behaviours may themselves assist with reducing alcohol use (Michie et al., 2012). To control for this effect, and thereby ensure that we can specifically attribute any positive effects to the inclusion of ApBM training (and not merely the effects of the data collection, which may not be present in a final version of the app that would be implemented clinically), the control version of the app includes the same self-report requirements as the ApBM version. A second consideration was ensuring blinding: if participants in the control condition know they are in a control condition, this may bias outcomes both due to expectancy effects and due to differential rates of drop-out (as participants may be less likely to remain motivated to continue participating if they know they are not receiving an intervention). If control participants were only asked to self-report weekly alcohol use, it is likely they may guess they are not in an intervention condition and, as such we have included a weekly sham-training task (which also functions as an approach bias measurement task), so that participants in both conditions can be told they are completing an “attention control” task.

Aims and Hypotheses

We aim to determine whether providing the “active” version of AAT-App (including ApBM) to people accessing outpatient alcohol treatment from AOD services, is effective, relative to a minimal version of the app which does not include ApBM training, at reducing alcohol use, cravings, and severity of dependence. We also aim to test the psychometric properties of the mobile phone approach bias measure we developed, and whether engaging in AAT-App significantly reduces approach bias, relative to the minimal control condition. We also aim to explore user experiences of AAT-App’s, perceived alignment with treatment, and suggested improvements, using qualitative interviews in a subset of participants, to guide further future improvements to the app and its implementation.

We hypothesise that:

Primary outcome:

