In the AAT, participants are presented with 20 images of alcohol and 20 neutral images (e.g., stationary, office ware, road signs, kitchenware, etc.) which are presented once in a white landscape orientation picture frame, and once in a white portrait orientation frame (for a total of 80 image presentations). Images are presented one by one, in a quasi-random order (with a maximum of three consecutive images appearing in the same category or orientation), and images are fixed (i.e., there is no option to personalise/select which images are presented in the task). When the frame is in landscape orientation, the participant is required to swipe downwards (i.e., towards themselves), which (if the movement is at least 40 pixels downward) causes the picture to expand, increasing to 600 x 600 pixels over a period of 500 milliseconds (ms), as if the participant has “pulled” the picture “towards” themselves. When the frame is in portrait orientation, the participant is instructed to swipe upwards (i.e., away from themselves), which (if the movement is at least 40 pixels upwards) causes the picture to shrink until it disappears, which takes 500 ms, as if they have “pushed” it “away”. If the participant swipes (at least 40 pixels) in the wrong direction, a red “X” is displayed to inform them that they made an error. After the picture expands/shrinks to its maximum/minimum extent, there is a 250 ms inter-stimulus interval before presentation of the next picture.

Upon commencing the AAT, task instructions are displayed to participants, and they then complete 10 practice trials (including 5 images in portrait frames and 5 in landscape frames, in random order) to familiarise themselves with the task. Participants then respond to the 80 image presentations, and reaction time (ms) data for each image trial and its response category (alcohol-portrait, alcohol-landscape, neutral-portrait and neutral-landscape) is recorded.

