AAT trials will be considered valid if the initial response (i.e., swiping up or down) is correct and the reaction time is within 300-3000ms. Median reaction times of valid trials will be calculated separately for each of the 4 picture-response categories (i.e., alcohol-portrait, alcohol-landscape, neutral-portrait, neutral-landscape), if at least 70% of trials were valid. If less than 70% of trials are valid, the median for that picture-response category will be considered missing. For each picture type (alcohol or neutral), the median reaction time for "swipe-down" responses will be subtracted

from the median reaction time for "swipe-up" responses to quantify approach bias. As the psychometric properties of an AAT delivered via smartphone have not been previously established, and prior analyses of the psychometric properties of the AAT using other modes of delivery have yielded highly variable results (Kersbergen, Woud, & Field, 2015; Rinck et al., 2018), we will conduct our own analyses of this AAT's psychometric properties (described further below).

Quality of life and health: Participants will be asked to complete 3 items adapted from the Australian Treatment Outcomes Profile (ATOP) (Ryan et al., 2014) assessing psychological health, physical health, and overall quality of life over the past 28 days. Participants will be shown questions asking:

- "This question is about your psychological health during the past 4 weeks – this includes your overall mood, anxiety, depression, or any emotions or feelings that have been troubling you. How would you rate your psychological health?"
- "This question is about your physical health. Please think in an overall way about physical health problems, symptoms or illnesses that have bothered you during the past four weeks – this includes pain, breathing, stomach, sleep, mobility problems or other physical symptoms. How would you rate your physical health?"
- "This question is about how you see your overall quality of life. Please think in an overall way about your living conditions and circumstances, your family and other relationships, work and financial aspects of your life and your overall social situation. How would you rate your quality of life?"

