
Psychometric properties of AAT: The internal consistency of the AAT will be calculated by separately calculating Cronbach's α for the alcohol approach bias items and the positive approach bias items, following the method reported by Kersbergen, Woud and Field (2015). As such, we will calculate difference scores between each nth "swipe-up alcohol" trial and each nth "swipe-down alcohol" trial, deriving 20 difference scores for alcohol images. The same process will be used to derive difference scores for the 20 neutral images. Bootstrapping will be used to calculate 95% confidence intervals for Cronbach's α values. Test-retest reliability of alcohol approach bias and positive approach bias scores will be assessed in the control group by testing Pearson's correlations between scores from their first 2 AAT assessments (baseline and week 1). Exploratory analyses will also test Pearson's correlations between baseline alcohol approach bias scores and scores on measures of alcohol craving (CEQ-F scores; pre-session VAS craving scores), dependence severity (SDS; AUDIT),

and consumption (drinking days, heavy drinking days and standard drinks, using the in-app alcohol calendar).

Qualitative data: Interview transcripts will be subjected to a thematic qualitative analysis in order to identify underlying themes and patterns within each respondent's discourse. Thematic analysis will proceed according to the six stage process described by Braun and Clark (2006):

- 1 Familiarisation with the data: Reading and re-reading transcripts, noting initial ideas.
- 2 Coding: Deriving codes which label important features of the data that might be relevant to answering research questions. Then systematically attributing meaning throughout the dataset by identifying chunks of text with similar meanings and labelling them with corresponding codes.
- 3 Generating initial themes: Examining codes and collated data for broader patterns of meaning, using codes as building blocks to construct candidate themes (and promoting a code to a theme where appropriate), then collating data for each candidate theme to be "tested" in relation to research question or overall dataset.
- 4 Reviewing themes, checking them against the dataset to determine whether they tell a convincing story of the data that addresses the research questions; splitting, combining, and/or discarding themes as appropriate.

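### Cronbach's alpha on nth-trial differences is not the internal consistency of the median-based approach bias score that the trial analyses

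*Combined protocol and SAP*

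**What the plan says.** The task (Measures, Alcohol approach bias): "participants are presented with 20 images of alcohol and 20 neutral images", each shown once in each frame orientation, "for a total of 80 image presentations". That gives 20 trials in each of four picture-response categories.

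The score (same section): "AAT trials will be considered valid if the initial response (i.e., swiping up or down) is correct and the reaction time is within 300-3000ms". Then "Median reaction times of valid trials will be calculated separately for each of the 4 picture-response categories", "if at least 70% of trials were valid". Otherwise: "If less than 70% of trials are valid, the median for that picture-response category will be considered missing". Approach bias for a picture type is the swipe-up median minus the swipe-down median.

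The reliability analysis (Data Analysis, Psychometric properties of AAT): Cronbach's alpha is computed separately by picture type, following a cited method. The nth swipe-up trial is paired with the nth swipe-down trial, "deriving 20 difference scores for alcohol images" and likewise for neutral images, with bootstrap 95% confidence intervals. Test-retest Pearson correlations of the approach bias scores are planned in the control group between baseline and week 1.

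The purpose (Aims and Hypotheses): "We also aim to test the psychometric properties of the mobile phone approach bias measure we developed". Hypothesis 9 compares the change in approach bias between the groups.

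**The concern.** Alpha is a property of the sum, or equivalently the mean, of the items entered into it. Here the items are 20 single-trial differences, so alpha speaks for their mean. The trial analyses a difference of medians over a filtered set of trials. Medians and means of the same trials have different sampling error, so one reliability does not stand in for the other.

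The psychometric section also does not say whether the validity rule applies to the trials entering alpha, what happens to a pair with one invalid member, or whether n counts all trials or only valid ones. Some of these choices could restrict the calculation to a small and unusually accurate group.

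At stake are a stated aim and the reading of hypothesis 9. If no group difference in approach bias is seen, one needs to know how reliably the analysed score was measured. The plan itself says that this task's properties on a smartphone are not established.

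**Working it through.** **Inputs from the documents.** 20 alcohol and 20 neutral images, two orientations, a 70% validity threshold per category, a target of at least 300 participants. **Assumed, because the documents give none:** the per-trial validity rate p and the reaction-time distributions.

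**Step 1. The plan's own counts.** (20 + 20) × 2 = 80 presentations. Alcohol trials: 20 × 2 = 40, forming 20 up/down pairs. This reproduces the plan's 80 and 20. The threshold is 0.70 × 20 = 14 valid trials, so up to 6 of 20 may be dropped per category.

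**Step 2. What alpha measures.** Let the true bias have standard deviation s and let trial noise be normal (SD 80 ms) plus exponential (mean t). The noise variance per trial is 80² + t². A difference of two 20-trial means has error variance 2(80² + t²)/20, and its reliability is s² / (s² + error variance). With t = 20 the error variance is 2 × 6,800 / 20 = 680, so:
- s = 30: 900/1,580 = 0.570
- s = 50: 2,500/3,180 = 0.786
- s = 80: 6,400/7,080 = 0.904

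A simulation with these parameters (20,000 people, two parallel sessions, all trials valid) compared alpha with the between-session correlation of the median-based score:

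| s (ms) | t (ms) | Alpha | Median-score reliability | Gap |
|---|---|---|---|---|
| 30 | 20 | 0.571 | 0.483 | 0.088 |
| 50 | 20 | 0.786 | 0.711 | 0.075 |
| 80 | 20 | 0.904 | 0.866 | 0.038 |
| 30 | 150 | 0.240 | 0.234 | 0.006 |
| 50 | 150 | 0.462 | 0.469 | −0.007 |
| 80 | 150 | 0.690 | 0.685 | 0.005 |
| 30 | 300 | 0.098 | 0.091 | 0.007 |
| 80 | 300 | 0.394 | 0.409 | −0.015 |

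Alpha matches the mean-based formula. With near-normal noise it overstates the reliability of the median score; with strongly right-skewed noise the two nearly agree. With 5% of trials invalid at random, the largest gap was 0.566 − 0.459 = 0.107.

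**Step 3. Complete-case alpha, if the validity rule is applied.** With independent trials, P(all 40 valid) = p^40. P(both categories scoreable) = P(Binomial(20, p) ≥ 14)².

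| p | All 40 valid | Scoreable under the 70% rule | Complete cases out of 300 |
|---|---|---|---|
| 0.99 | 66.9% | 100% | 201 |
| 0.98 | 44.6% | 100% | 134 |
| 0.95 | 12.9% | 99.99% | 39 |
| 0.90 | 1.5% | 99.5% | 4 |

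The share falls below one half once p is under 0.5^(1/40) = 0.983. The last column uses the recruitment target, which is not the number who will complete the task.

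**Step 4. Sensitivity to independence.** If accuracy differs between people, more complete cases remain. For example, with p following a Beta(19, 1) distribution (mean 0.95), the expected share is 19/59 = 32%, or about 97 of 300, against 39 with a common p of 0.95.

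**Step 5. Other handling.** Alpha from pairwise covariances with 5% invalid trials was 0.783, the same as on all trials (s = 50, t = 20). It needs no complete cases, but it still describes the mean.

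**The case against.** The strongest reply has four parts.

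- The plan follows a published method, calls the result internal consistency, and does not claim that alpha is the reliability of the median score. That is so. But the aim is to test the measure, and the measure is the median-based score.
- The plan already has reliability evidence for the analysed score, because the test-retest correlation uses it. This stands in part. That evidence comes from controls only, over one week, and mixes real change with measurement error; it is not internal consistency.
- A reader might infer that alpha requires every one of 40 trials to be valid, and so excludes most participants. The documents do not support this. They are silent on invalid trials, and the cited method may settle the matter. The requirement follows only if the validity rule is applied and complete cases are used, and even then the loss depends on an unknown validity rate. This part stands in full.
- Spearman-Brown correction is derived for means of parallel parts, so it is also only approximate for medians. That is true. In simulations with the same assumed parameters, however, the corrected split-half mostly fell within about 0.03 of the median score's reliability, while alpha was too high by up to about 0.1 with near-normal noise.

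A reliability for an alcohol-minus-neutral score is not called for: the plan analyses the picture types separately.

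**Conclusion.** The mismatch is real on any handling of invalid trials: alpha describes a mean of trial differences, and the trial analyses a difference of medians over valid trials. Its likely size is modest, about 0 to 0.1 on the reliability scale, and it depends on how skewed the reaction times are, which is assumed here. The possible loss of participants in Step 3 is conditional on one unstated choice and should be read as a reason to state the handling, not as a forecast. The simulations made trials invalid at random, so they say nothing about bias from selecting accurate participants. The point touches a psychometric aim and the interpretation of hypothesis 9. It does not touch the primary outcome, and no planned analysis is made conditional on alpha. It is a worthwhile improvement rather than a necessary correction.

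**What to change.** Add to Psychometric properties of AAT a repeated random split-half reliability, separately for the alcohol and the neutral scores:

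1. Take participants who meet the 70% rule in both categories of the picture type.
2. Randomly split the valid trials within each picture-response category into halves, and form the swipe-up minus swipe-down difference of medians in each half.
3. Correlate the halves across participants, apply the Spearman-Brown correction (noting that it is approximate for medians), and average over many splits.
4. Give a bootstrap 95% confidence interval, resampling participants.

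Applying the 70% rule to the whole category before splitting avoids having to define it for halves.

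Keep alpha for comparability with the cited method. State whether invalid trials enter it, how incomplete pairs are treated, whether n counts all or only valid trials, and how many participants contribute.

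The cost is one paragraph, a short script and a second reliability figure to report and explain. No new data are needed: Data management lists trial-level reaction time, trial type and errors among the stored data.

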- **[if no to previous question]** What was your old mobile number (the one you originally used when signing up to the study)?

RECORDER OFF

RECORDER ON

SECTION B: INTERVIEW

[Main dot-points represent the primary interview questions, sub-dot-points represent suggested prompts or follow-up questions that may be used as appropriate]

- To start off, I'm interested in knowing about what kind of treatment you were getting for alcohol use when you decided to try AAT-App. Can you tell me about that?
 - How long had you been involved in that treatment?
 - How were those treatments going for you?
- And what made you want to try AAT-App?
 - Can you describe the concerns you had about your alcohol use when you decided to use AAT-App?
 - Can you describe what was going on in your treatment when you decided to try AAT-App?
- Tell me about your experience using AAT-App. How'd you find it?
 - What were the positives/negatives?
 - Any bugs or glitches that came up?
- How (or in what contexts) did you use the brain-training app?
 - Did you use it at any particular times or places?
 - Did you try using it for immediate craving relief/support when urges to drink arose and, if so, how did that go?
- Can you tell me about any effects that AAT-App had on your alcohol cravings or drinking?
 - *[If they felt it was helpful]* When did you notice it helping?
- Do you have any thoughts about how AAT-App combined with the treatment you were receiving?
- What was your understanding of how the brain-training is supposed to work?
 - What do you think about the information provided in the app about how the brain-training works (if you can remember it)?
 - What influence, if any, do you think that knowing the theory behind the brain-training has on how the app worked (or didn't work) for you?
- What images did you choose to use for the brain-training?
 - [prompt for information regarding both positive and alcohol images if they only describe one category]
 - Did you use your own photos, or the ones provided in the app?
 - *[If they used photos provided in the app]* What did you think of the photo options provided in the app? (Do you have any suggestions about changes to the options?)

- What guided your decision about which photos to use?
- Do you have any suggestions for how the app could be improved?
- Do you have any other thoughts or opinions about the app that you would like to share?

Conclusion

Thanks, we've covered a lot today and I appreciate you sharing your thoughts about your experiences with the app. We really value hearing people's feedback, so your input is a huge help!

RECORDER OFF

End of interview wellbeing check:

Finally, after everything we've discussed, I just wanted to make sure that you're ok and don't have any concerns by anything we've talked about today?

- No concerns Requires support – proceed to support option (see Lifeline, DirectLine, and Counselling Online details on participant information sheet)

Arrange eVoucher to be texted or emailed to participant

And I'd just like to check whether you'd prefer your \$40 voucher be texted or emailed to you?

- Text Email

Brilliant. I'll arrange to get that sent to you ASAP, and thanks again for participating in the study and doing the interview with me today. Take care!

Labelling of interview file

Check participant's phone number and determine corresponding access code. Label the interview file with this access code.
